# Change from baseline to Week 12 in EDE-Q7 global score and 3 subscales

Changes from baseline in EDE-Q7 scores will be analyzed using a mixed model for repeated measurements as described for the primary endpoint, but with less time points.

# CGI-C score at Week 12

CGI-C scores will be compared between treatment groups using the Kruskal Wallis test.

# Improvement according to CGI-C at Week 12

This variable will be analyzed using a logistic regression model with a factor for treatment group. The relationship between improvement according to CGI-C at Week 12 and the primary efficacy outcome will be investigated.

# PGI-C score at Week 12

This variable will be analyzed using same methods as for CGI-C score at Week 12.

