presents three subscales: compulsive/obsessive (Items #1, 2, 3, 6, 7 and 8), restraint (Items #4 and 9), and control (Items #5 and 10).

The HAMD-17 is an indicator of depression and anxiety. The HAMD-17 consists of 17 items, with most items providing a score that ranges between 'Absent' and 'Almost all the time'. The MPS sub-score combines items 1 (depressed mood), 2 (guilt), 7 (work and activities), 8 (psychomotor retardation), 9 (psychomotor agitation), and 10 (anxiety, psychic).

EDE-Q7 is a self-reported questionnaire containing 7 of the 28 questions from the EDE-Q about eating behaviors (Items #1, 3, 4, 22, 23, 25 and 26). The EDE-Q7 presents three subscales: dietary restraint (Items #1, 3 and 4), shape/weight overvaluation (Items #22 and 23), and body dissatisfaction (Items #25 and 26).

The CGI-C is a 1-item, 7-point scale that ranges from "Very much improved" to "Very much worse".

The PGI-C is a 1-item, 7-point scale that ranges from "Very much improved" to "Very much worse".

The CGI-S is a 1-item, 7-point scale that ranges from "Normal, not at all ill" to "Among the most extremely ill patients".

The PGI-S is a question concerning the overall severity of symptoms and impact that the study participant may have experienced due to his/her BE episodes over the 7 days preceding the PGI-S completion. It ranges from "No binge eating" to "Severe".

The exploratory efficacy endpoints will be tested at two-sided 5% significance level. No further Type I error control is applied; hence, these analyses are to be considered descriptive.

The MMRM [Section 6.1.3], will be fitted for:

- The change from baseline to Week 12 (EOT) in the number of BE episodes per week, with a covariate for the baseline number of BE episodes (rather than the number of BE days) per week.
- The change from baseline to Week 12 (EOT) in EDE-Q7 global score and 3 subscales, with a covariate for the time points limited to Week 4 (Visit 5), Week 8 (Visit 7), and Week 12 (EOT).
- The change from baseline to Week 12 (EOT) in the total score of the YBOCS-BE and in the subscales scores (i.e., compulsive/obsessive, restraint, control), with a covariate for the time points limited to Week 4 (Visit 5), Week 8 (Visit 7) and Week 12 (EOT).

ACT-539313		Statistical Analysis Plan
ID-082A201	Confidential	for Clinical Study Report
1 April 2022, page 31/60	Confidential	Version 3
		Doc No D-22.100

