• The change from baseline to Week 6 (Visit 6) and to Week 12 (EOT) in the HAMD-17 total score, subitems 10 and 11, and MPS score, with a covariate for the time points limited to Week 6 (Visit 6) and Week 12 (EOT).

Absence of BE episodes will be analyzed using a logistic regression model with a factor for treatment group, sex and BMI category, and a covariate for the baseline number of BE episodes per week. For study participants who discontinued treatment prematurely, the outcome will be set to 'No absence'.

The CGI-C and PGI-C scores at Week 12 (EOT) will be compared between treatment groups using the Kruskal-Wallis test. Missing assessments at Week 12 will be imputed using last on-treatment observation carried forward.

The change from baseline to Week 12 (EOT) in the CGI-S score, PGI-S score, body weight and HbA1c will be analyzed using an ANCOVA model with a factor for treatment group and a covariate for baseline score. Missing assessments for CGI-S and PGI-S score at Week 12 will be imputed using last on-treatment observation carried forward.

The improvement according to CGI-C score at Week 12 (EOT) will be analyzed using a logistic regression model with a factor for treatment group.

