     mnar adjust(obst5 / shift=&sj adjustobs=(TRT = 'ACT-539313 100 mg'));
     mnar adjust(obst6 / shift=&sj adjustobs=(TRT = 'ACT-539313 100 mg'));
     var TRT ASEX BMIGR BASE obst1 obst2 obst3 obst4 obst5 obst6;
run;
data outmi;
     set outmi;
     Shift= &sj;
run;
data &out;
     set &out outmi;
run:
%end:
%mend midata;
```

```
%midata(data=fin_mi_mono, smin=0, smax=2, sinc=0.25, out=be5);
```

The 9 study participants forced to discontinue due to site closure will be imputed using MAR assumption setting the seed to 295104.

14.6 SAS[®] code for logistic regression of absence of BE episodes during the last 4 weeks of treatment

This model adjusts for baseline number of BE days (BASE), sex (SEX), BMI as categorical variable (BMIGR), and treatment (TRT). Reference categories are placebo for treatment and obese (BMI \ge 30) for BMI. Example SAS[®] statements for the analysis are:

```
proc logistic data=data;
      class TRT (ref='PLACEBO') SEX BMIGR (ref='OBESE');
      model Y (event='1') = TRT SEX BMIGR BASE / clodds=wald orpvalue;
run;
```

ACT-539313		Statistical Analysis Plan
ID-082A201	Confidential	for Clinical Study Report
1 April 2022, page 52/60	Confidential	Version 3
		Doc No D-22.100

This code provides confidence limit for the proportion of study participants with and without absence of BE episodes during the last 4 weeks of treatment.

proc freq data=data; table Y / binomial(level='1'); by TRT;

run;

14.7 SAS[®] code for logistic regression of improvement according to CGI-C score at Week 12

This model adjusts only for treatment (TRT) and the reference category is placebo. Example $SAS^{(R)}$ statements for the analysis are:

```
proc logistic data=data;
      class TRT (ref='PLACEBO');
      model Y2 (event='1') = TRT / clodds=wald orpvalue;
run;
```

run;

This code provides confidence limit for the proportion of study participants with and without improvement according to CGI-C score at Week 12.

proc freq data=data; table Y / binomial(level='1'); by TRT;

run;

14.8 SAS[®] code for Kruskal-Wallis test of CGI-C and PGI-C scores at Week 12

Example SAS[®] statements for the analysis are:

```
proc npar1way data=data wilcoxon;
class TRT;
var CGI-C; /* this will be updated with PGI-C for PGI-C analysis */
```

run;

14.9 SAS[®] code for ANCOVA of change from baseline to Week 12 in CGI-S score, PGI-S score, body weight and HbA1c

This model is used for some exploratory efficacy endpoints. Example SAS[®] statements for the analysis are:

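### The CGI-C improvement model is the only efficacy regression in the SAP without a baseline covariate; adding baseline CGI-S would be a cheap, small improvement, not the correction of an error

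*SAP*

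**What the plan says.** For the CGI-C responder endpoint (much or very much improved at Week 12, missing counted as not improved), SAP 6.3 says: "The improvement according to CGI-C score at Week 12 (EOT) will be analyzed using a logistic regression model with a factor for treatment group". The description of the code in SAP 14.7 confirms it: "This model adjusts only for treatment (TRT) and the reference category is placebo". Protocol 9.2.4.2 has the same model: "This variable will be analyzed using a logistic regression model with a factor for treatment group". SAP 14.7 also asks for confidence limits on the proportion in each arm, but for no difference between arms.

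The other responder endpoint, absence of BE episodes, is fitted with "a logistic regression model with a factor for treatment group, sex and BMI category, and a covariate for the baseline number of BE episodes" (SAP 6.3, where the count is a weekly rate; same in Protocol 9.2.4.2). Neither document says why the two responder models differ.

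On the status of these analyses, SAP 6.3 says: "No further Type I error control is applied; hence, these analyses are to be considered descriptive".

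**The concern.** The efficacy regressions in SAP 6 compare as follows:

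- MMRM for BE days (primary), BE episodes, EDE-Q7, YBOCS-BE and HAMD-17: baseline value included.
- ANCOVA for CGI-S, PGI-S, body weight and HbA1c: baseline value included.
- Logistic model for absence of BE episodes: baseline BE frequency included.
- Logistic model for CGI-C improvement: treatment only.

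The Kruskal-Wallis comparisons of CGI-C and PGI-C scores also have no covariate, but they are rank tests, not regressions.

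A suitable covariate is at hand. CGI-S is rated at Visits 1 and 2 and must be at least 4 at both (Protocol 5.3), so no randomized participant should lack it. Protocol 5.2 cites placebo response of 26% to 38% in BED trials, higher where eating pathology was milder at entry. Randomization is unstratified with about 60 per arm (Protocol 6.1.3), so the arms may differ by chance in baseline severity, and this model does not take that into account. At stake is a little efficiency on one exploratory endpoint.

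**Working it through.** **1. The plan's own figures.** The documents give no power, response rate or precision for CGI-C improvement. The only power figures are for the primary endpoint (Protocol 9.4, Table 6). With power = Φ(d·√(n/2) − 1.96) and n = 60 per arm, effect sizes 0.5, 0.6 and 0.7 give 78.2%, 90.8% and 97.0%, against 78%, 91% and 97% stated. They reproduce, but they do not bear on CGI-C. Everything below therefore rests on assumptions.

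**2. What adjustment does to a log odds ratio.** Simulated trials, about 3,000 per scenario, 60 per arm. Treatment-only model against treatment + sex + BMI category + standardised baseline. Assumed: placebo improvement 30%, 40% or 50%; conditional log OR 1.0; 80% female; 65% with BMI ≥ 30; log-odds effects of baseline (per SD), sex and BMI of 0/0/0 (none), 0.3/0.2/0.2 (weak), 0.6/0.4/0.4 (moderate) or 1.0/0.5/0.5 (strong).

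Check of the unadjusted SE at 40% vs 64.4%: √[1/(60·0.4·0.6) + 1/(60·0.644·0.356)] = √(0.0694 + 0.0727) = 0.377; the simulated mean is 0.381.

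Results at 40% on placebo (mean log OR / mean SE = ratio):

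| Covariates | Unadjusted | Adjusted | Power |
|---|---|---|---|
| none | 1.029/0.381 = 2.70 | 1.059/0.393 = 2.69 | 79.7% → 78.3% |
| weak | 1.002/0.381 = 2.63 | 1.059/0.398 = 2.66 | 78.0% → 77.3% |
| moderate | 0.926/0.379 = 2.44 | 1.046/0.413 = 2.53 | 71.3% → 72.7% |
| strong | 0.828/0.377 = 2.20 | 1.056/0.440 = 2.40 | 61.0% → 67.2% |

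The SE rose in every simulated trial, by 3% to 17% on average. Where power rises, it is because the conditional log OR lies further from zero by more than the SE grows.

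Across placebo rates of 30% to 50%, the power change is −0.4 to −1.4 points (none), −0.7 to +0.3 (weak), +1.4 to +3.5 (moderate) and +6 to +9 (strong). The SD of the standardised risk difference is about 1% larger (none), within 1% (weak), 2–3% smaller (moderate) and 7–8% smaller (strong). Under the null, rejection is 5.2–5.5% unadjusted and 5.3–5.6% adjusted.

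**3. Which scenario is credible.** A log-odds effect γ per SD of baseline corresponds to a latent correlation of γ/√(γ² + π²/3): 0.3 gives 0.3/√3.38 = 0.16, 0.6 gives 0.6/√3.65 = 0.31, and 1.0 gives 1.0/√4.29 = 0.48. The strong case therefore lies above the assumed range of 0.2 to 0.4.

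**4. A single baseline covariate.** With improvement assumed at 65% vs 40%, and a normally distributed baseline with latent correlation 0.2, 0.3 or 0.4, power moves from 80% to 80%, 82% or 83%. With CGI-S confined to 4–7, as the entry criterion requires, power changes by about −1.5 to +3 points and the SD of the standardised risk difference by about +1% to −5%. Type I error stays near 5%, and sex and BMI category add nothing further.

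**The case against.** The case for leaving the model alone is strong, and much of it stands.

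- *The unadjusted test is valid.* Under 1:1 unstratified randomization no stratification factor has to be carried into the model, and its error rate already reflects chance imbalance. A reader might infer from the missing stratification that the estimate is biased; the documents do not support that, and simulated Type I error is near 5% either way.
- *There is no contradiction.* Protocol 9.2.4.2, SAP 6.3 and SAP 14.7 specify the same model.
- *CGI-C is already a rating of change from the starting state* (Protocol 7.2.4.4), and the entry rule leaves baseline CGI-S only the values 4 to 7. Both may weaken its prognostic value. This is why the gain is put at 0 to 3 points and not at the strong-covariate figure.
- *The CGI and PGI analyses are kept simple throughout*: rank tests, and ANCOVA without sex or BMI. This speaks against importing the whole covariate set of the absence-of-BE model, but not against a baseline score, which the CGI-S and PGI-S ANCOVAs include.
- *The absence-of-BE model is an unsettled template.* Its baseline covariate is BE episodes in SAP 6.3 but BE days in the description in SAP 14.6. That has to be reconciled separately, and it is a reason not to copy the model.

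What remains is that CGI-C improvement alone lacks a baseline covariate, no reason is given, and the covariate is already collected.

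**Conclusion.** This is an optional improvement; nothing in the plan is wrong as written. If baseline CGI-S has a latent correlation of 0.2 to 0.4 with improvement, adjusting for it gives about 0 to 3 points of power and up to about 5% lower SD of the standardised risk difference. If it is unrelated, the cost is about 1 point of power. The response rates, covariate effects and correlations are all assumed. The only support in the documents is the general statement in Protocol 5.2 on baseline severity and placebo response, which does not concern CGI-C specifically.

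A reader might infer that the unadjusted model gives away precision at no cost. That does not hold for the odds ratio: its standard error increases on adjustment, and the target changes from a marginal to a conditional odds ratio. Any gain appears in power, or in the standardised risk difference. As the endpoint is descriptive and no power was planned for it, no trial decision depends on the change.

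**What to change.** In SAP 6.3 and 14.7, before unblinding:

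- Add baseline CGI-S to the CGI-C improvement model. Sex and BMI category are optional and add little.
- State that the resulting odds ratio is conditional on baseline CGI-S.
- Report the standardised (marginal) risk difference with its 95% CI: the average over all participants of the predicted probability of improvement under ACT-539313 minus that under placebo, with the interval from the delta method or a bootstrap.
- Keep the treatment-only result as a supportive analysis.

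The cost is one line of SAP text, one added model term and a short standardisation step. No new data are needed: CGI-S is an entry requirement, and missing CGI-C is already counted as not improved, so no participant should drop out of the model. If the sponsor prefers the planned model, one sentence explaining why this responder analysis alone is unadjusted would be enough.

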7 SAFETY VARIABLES AND ANALYSES

7.1 Overview of safety analyses including subgroup analyses

The SAF will be used for tables and listings of safety data, unless otherwise stated.

Unless noted otherwise, only the treatment-emergent safety data will be considered in tables and figures.

All safety data described below will be listed.

7.2 Adverse events

TEAEs are defined as AEs that started or worsened on or after study treatment start date up to the EOS.

AEs will be coded using MedDRA. The MedDRA version used for reporting will be specified in the footnote of the applicable output.

The number (%) of study participants experiencing a TEAE (including SAEs, AESIs, AEs leading to premature discontinuation and/or temporary interruption of study treatment) will be summarized by SOC and/or PT, and/or maximum intensity.

ACT-539313		Statistical Analysis Plan
ID-082A201	Confidential	for Clinical Study Report
1 April 2022, page 32/60	Confidential	Version 3
		Doc No D-22.100

AESIs, defined as AE PTs denoting *somnolence* and *fatigue* will be summarized separately [Section 14.13]. Additionally, this summary will be provided by 2-week interval (Week 1–2 until Week 11–12).

A subject with multiple intensities reported for an AE will be summarized under the maximum intensity recorded for the event.

Apart from the summaries of occurrences, where each event is counted, a subject with multiple occurrences of an AE is counted only once in the AE category (e.g., SOC, PT). If a single AE worsens on the same treatment group, then this event will be considered as one occurrence.

AEs will be sorted by descending frequency, first in the ACT-539313 group, then in the placebo group. After this sorting, SOCs are presented in alphabetical order and PTs are sorted alphabetically within each SOC.

The following AE summary tables will be provided:

- Treatment-emergent AEs.
- Treatment-emergent AEs during the treatment period^a.
- TEAEs during the treatment period^a related to study treatment.
- AEs leading to premature discontinuation of study treatment.
- AEs leading to temporary interruption of study treatment.
- Treatment-emergent SAEs (including occurrences).
- Treatment-emergent SAEs related to study treatment (including occurrences).
- Treatment-emergent AESIs.
- Treatment-emergent AEs during the safety follow-up period.
- TEAEs with fatal outcome.
- TEAEs related to study treatment with fatal outcome.
- Total number of deaths.

^a Includes only those TEAEs occurring (i.e., that started or worsened) during the treatment period [see Section 11.2].

All AEs will be listed, and AESI and SAE will be flagged in the AE listing.

Separate listings will be provided for AEs leading to premature discontinuation of study treatment, AEs leading to temporary interruption of study treatment, SAEs and AESI.

All deaths will be listed, with cause of death, using the SCR set.

ACT-539313		Statistical Analysis Plan
ID-082A201	Confidential	for Clinical Study Report
1 April 2022, page 33/60	Confidential	Version 3
		Doc No D-22 100

An AE listing, using the SCR set, will also be provided for study participants who were not randomized (i.e., screen failures) and study participants who were randomized but did not take study treatment. This listing will therefore include any study participants who discontinued the study due to AE but did not receive any study treatment.

Any other summary required for disclosure to public database will be generated as appropriate.

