	• Occurrence of suicidal ideation and/or behavior while on study treatment based on the C-SSRS © from baseline to all assessed time points during the study up to EOS.		
Other exploratory objectives			
To assess the PK of ACT-539313	• ACT-539313 plasma concentrations prior to morning dosing at Week 4, Week 8, and Week 12.		

a A treatment-emergent AE is any AE temporally associated with the use of study treatment (from study treatment start up to EOS, whether or not considered by the investigator as related to study treatment).

b A treatment-emergent marked laboratory abnormality or medically relevant ECG abnormality is any marked laboratory abnormality or medically relevant ECG abnormality temporally associated with the use of study treatment (from study treatment start to all assessed time points during the study). The selection of marked/medically relevant abnormalities considered for the analyses will be based on standard definitions and described in the SAP.

AE = adverse event; AESI = adverse event of special interest; BE = binge eating; BED = binge eating disorder; CGI-C = Clinical Global Impression of Change scale; CGI-S = Clinical Global Impression of Severity scale ; C-SSRS© = Columbia Suicide Severity Rating Scale; ECG = electrocardiogram; EDE-Q7 = Eating Disorder Examination Questionnaire (7-item); EOS = End-of-Study; EOT = End-of-Treatment; HAMD-17 = Hamilton Rating Scale for Depression (17-item); FERT = Facial Expression Recognition Task; HbA1c = glycated hemoglobin; MPS = Maier-Philipp subscale; PGI-C = Patient Global Impression of Severity; PT = preferred term; SAE = serious adverse event; SAP = statistical analysis plan; SSS = Stanford Sleepiness Scale: TEAE = treatment-emergent adverse event; YBOCS-BE = Yale-Brown Obsessive-Compulsive Scale modified for Binge Eating

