# 8.1.4 Relationship to study treatment

Each AE/SAE must be assessed by the investigator/delegate as to whether or not there is a reasonable possibility of causal relationship to the study treatment and reported as either related or unrelated.

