# 8.2 **Reporting procedures**

# 8.2.1 Reporting and follow-up of AEs

The occurrence of an AE may come to the attention of study personnel during study visits, telephone calls, or interviews of study participants presenting for medical care.

At each study visit (scheduled or unscheduled), the investigator/delegate will inquire about the occurrence of AEs since the last visit.

All AEs with an onset date after signing of the ICF up to EOS must be recorded in the eCRF.

The AE should be reported as a final diagnosis (if possible) rather than a list of symptoms.

Information to be collected on an AE form in the eCRF includes date of onset, time of onset, action taken with the study treatment, outcome of the AE, date and time of resolution (if applicable), and PI/delegate's assessment of intensity as well as its relationship to study treatment or protocol-mandated procedures.

Information on worsening of intensity will be collected. If the AE lessens in intensity, no change in the severity is required to be reported.

AEs still ongoing after study treatment discontinuation must be followed up until resolution, until they are no longer considered clinically relevant, or until stabilization.

ACT-539313 Binge Eating Disorder Protocol ID-082A201 Final Version 3 4 May 2021, page 80/140

Confidential

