# 9.2.6 Adverse events

# 9.2.6.1.1. TEAEs and SAEs

TEAEs and SAEs, including AESIs, will be tabulated by study treatment, SOC, and preferred terms within each SOC: the number and percentage of study participants who experienced at least one (S)AE, at least one (S)AE within each SOC, and at least one (S)AE within each preferred term will be displayed. (S)AEs will also be summarized by decreasing frequency of preferred term. (S)AEs will also be tabulated by maximum intensity and by relationship to study treatment.

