7.7 Withdrawal symptoms

7.7.1 Benzodiazepine Withdrawal Symptoms Questionnaire

The BWSQ consists of 20 items with each item rated by the subject as either 0 (No), 1 (Yes-moderate), or 2 (Yes-severe). The change in BWSQ Total score (possible range: 0 to 40) from the last available assessment during the treatment period to EOS will be summarized. Observed values will also be summarized.

The number (%) of study participants with a BWSQ Total score above 20 will be tabulated by visit (EOT and EOS).

The number (%) of study participants with one or more BWSQ symptom scored as 'severe' will be tabulated by visit (EOT and EOS).

In addition, withdrawal symptoms after study treatment discontinuation will be assessed through the incidence of AEs occurring during the safety follow-up period. As described in the respective section [Section 7.2], the incidence of AEs occurring during the safety follow-up period will be summarized.

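### SAP 7.2 limits its only general table of treatment-related TEAEs to the treatment period, whereas the protocol tabulates TEAEs, defined up to EOS, by relationship

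*SAP*

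**What the plan says.** **Protocol.** The footnote to Table 2 (Section 3) sets the window: "A treatment-emergent AE is any AE temporally associated with the use of study treatment (from study treatment start up to EOS". Section 8.2.1 collects events over all of it: "All AEs with an onset date after signing of the ICF up to EOS must be recorded in the eCRF". Section 8.1.4 requires a causality judgement for every event, serious or not: "Each AE/SAE must be assessed by the investigator/delegate as to whether or not there is a reasonable possibility of causal relationship to the study treatment". Section 9.2.6.1.1, which covers TEAEs and SAEs, then adds (opening bracket dropped): "S)AEs will also be tabulated by maximum intensity and by relationship to study treatment". It does not limit this to the treatment period.

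**SAP.** Section 7.2 uses the same window: "TEAEs are defined as AEs that started or worsened on or after study treatment start date up to the EOS". Its list of 12 AE tables has one general table for related events: "TEAEs during the treatment period^a related to study treatment". The footnote marked there reads "Includes only those TEAEs occurring (i.e., that started or worsened) during the treatment period", and it points to the study periods in Section 11.2. Two other tables select related events, one for SAEs and one for fatal TEAEs; neither is limited to the treatment period. TEAEs in safety follow-up have their own table, with no split by relationship. Section 7.7.1 uses those events as well: "withdrawal symptoms after study treatment discontinuation will be assessed through the incidence of AEs occurring during the safety follow-up period".

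**Declared changes.** SAP 12.1 records only a change of analysis sets for demographics and disease characteristics. Sections 12.3 and 12.4 are marked as not applicable.

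**The concern.** The protocol commits to showing relationship for TEAEs, and both documents run TEAEs to EOS. The SAP keeps the definition but stops its general relationship table earlier, with no reason given and no entry among the changes.

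The SAP is also uneven. All-cause TEAEs get both a table up to EOS and a treatment-period table. Related SAEs and related fatal TEAEs are not cut at the end of treatment. Only the general related table is.

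Two things are at stake. First, the number of participants with a related TEAE up to EOS is never produced, and a reader who takes the treatment-period count for it may take a figure that is too low. Second, the investigator's attribution of events that start after treatment is collected but not summarised by arm. This matters somewhat more here than in most trials, because withdrawal symptoms on stopping are a named safety endpoint in protocol Table 2 and SAP 7.7.1 looks to follow-up AEs as supplementary evidence on them.

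**Working it through.** There is no stated figure to reproduce. The check traces one event through the planned tables and then sizes the uncovered window in days.

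**Step 1. A test event.** Take a non-serious, non-fatal TEAE judged related, with onset in safety follow-up. Under both documents it is a TEAE, because onset is before EOS.

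**Step 2. The 12 tables in SAP 7.2.**

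| Table | Limited to treatment period? | Related events only? | Holds the test event? |
|---|---|---|---|
| All TEAEs | No | No | Yes |
| TEAEs in the treatment period | Yes | No | No |
| Related TEAEs in the treatment period | Yes | Yes | No |
| AEs leading to discontinuation; to interruption (2 tables) | Not stated | No | No, treatment has already ended |
| Treatment-emergent SAEs | No | No | No, not serious |
| Related treatment-emergent SAEs | No | Yes | No, not serious |
| AESIs | No | No | Only if its preferred term is in SAP Table 10 |
| TEAEs in safety follow-up | Follow-up only | No | Yes |
| Fatal TEAEs; related fatal TEAEs; deaths (3 tables) | No | The second only | No |

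The event reaches at least two all-cause tables and the AE listing, but none of the three tables that select related events. The general sentence in SAP 7.2 offers summaries by SOC, preferred term and maximum intensity, not by relationship. The provision for further public-disclosure summaries does not commit to such a table either.

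**Step 3. Uncovered days for a completer.** Inputs: EOT on Day 85 (protocol Table 1) and EOS 10 ± 3 days after EOT. Share uncovered = follow-up days / (85 + follow-up days).

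- 7 days: 7/92 = 7.6%
- 10 days: 10/95 = 10.5%
- 13 days: 13/98 = 13.3%

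Counting 84 treatment days instead gives 7/91 = 7.7% to 13/97 = 13.4%, so the choice makes no practical difference.

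**Step 4. Uncovered days for an early discontinuer.** Protocol 5.9.1 asks for an EOT visit 1 to 5 days after the last dose. SAP 11.2 ends the treatment period at EOT or, for discontinuers, whom it describes as lacking an EOT date, at the treatment end date. Two readings follow.

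- The period ends at the EOT visit: 7 to 13 days are uncovered.
- The period ends at the last dose: 1 + 7 = 8 to 5 + 13 = 18 days are uncovered.

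The start of follow-up is also inconsistent. SAP Section 2 and protocol 4.1.1 start it the day after the last dose; SAP 11.2 starts it the day after EOT. If the treatment period ends at the last dose and follow-up starts after the EOT visit, the days between belong to neither period. Events then would be in neither period-specific table. On any reading the uncovered share exceeds a completer's, because fewer days were spent on treatment.

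**The case against.** The best case for the SAP has four parts.

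1. **The window is inferred.** The protocol sentence on relationship names no period; the EOS limit comes from the TEAE definition. Protocol Section 9 leaves full details of analyses and displays to the SAP. This has some force. But the sentence stands in a section on TEAEs, and that term has a defined window in both documents. A narrower table is at least a departure to be noted in SAP 12.1.

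2. **The table is honest.** Its title states its period. That stands. A reader might infer that a headline safety count is wrong, but nothing in SAP 7.2 gives this table headline status, and it reports correctly what it says it reports. Participants are counted once, so the any-related total would change only for someone whose sole related TEAE is non-serious and starts after the treatment period. No event rate is available to say how often that happens.

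3. **Withdrawal does not depend on it.** Protocol Table 2 measures withdrawal by change in BWSQ and HAMD-17 from Week 12/EOT to EOS, and SAP 7.7 analyses both. Follow-up AEs are an addition, and their all-cause incidence by arm is arguably the stronger comparison in a blinded trial. This stands and limits the consequence.

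4. **Some off-drug events are captured.** A reader might infer that the related table misses every withdrawal-type AE by construction. The documents do not support that. SAP 5.4.2 allows for treatment interruptions (its examples last 4 and 7 days), and these lie inside the treatment period. On one reading of SAP 11.2, so do the days between a discontinuer's last dose and the EOT visit. Serious related events are tabulated whenever they start before EOS.

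None of this supplies a by-arm count of related TEAEs up to EOS.

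**Conclusion.** The mismatch is real and undeclared. A non-serious related TEAE that starts after the SAP treatment period is in no related-AE table. For completers the uncovered span is the last 7 to 13 days, about 8% to 13% of the TEAE window; for early discontinuers it is 7 to 13 or 8 to 18 days, depending on how SAP 11.2 is read. These are shares of calendar time, not of events. The effect on the count could be nil, and it is probably small.

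It would be wrong to say that the events are lost: they are in the all-TEAE table, the follow-up table and the listing. What is missing is the investigator's attribution, summarised by arm. No efficacy result and no all-cause safety table is affected.

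The conclusion rests on reading protocol 9.2.6.1.1 with the protocol's own TEAE definition, and on taking the SAP 7.2 table list as complete. The change is worth making because the protocol plans the tabulation and the data are already collected.

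**What to change.** - In SAP 7.2, add a table of TEAEs up to EOS related to study treatment, by arm. Keep the treatment-period version as a labelled subset.
- Split the table of TEAEs in safety follow-up by relationship.
- If the sponsor prefers to keep the restriction, declare it in SAP 12.1 with the reason.
- Reconcile SAP 11.2 with SAP Section 2 and protocol 4.1.1 and 5.9.1 on where the treatment period ends and follow-up begins for early discontinuers, so that each event between last dose and the EOT visit is assigned to exactly one period.

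The cost is one extra table shell, a split on a variable already in the database and a clarified definition. The related-TEAE count up to EOS may be slightly higher than the treatment-period count; showing both makes the difference visible.
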